## **6.9. Concomitant Medications and Non-Drug Therapies**

### **6.9.1. Permitted Medications and Non-Drug Therapies**

#### **6.9.1.1. Concomitant Medications**

All subjects can be given paracetamol, with caution during the study but administration time must be recorded in the eCRF. Allowable antibiotics are penicillins, cephalosporins, carbapenems and aminoglycosides (please refer to Section 12.5, Appendix 5). If the investigator considers that other antibiotics are required, the Medical Monitor should be consulted on a case by case basis.

Antiemetic choice should be based around the risk of further QTc prolongation over and above that which may be caused by DHA-PQP and in line with the approved prescribing information for DHA-PQP (refer to SRM).

All concomitant medications (prescription and non-prescription) taken during the study should be recorded in the eCRF. The minimum requirement is drug name, date of administration and reason for administration.

#### **6.9.1.2. Rescue Medication**

Subjects diagnosed with *P. vivax* relapse (i.e. a positive blood smear with or without vivax symptoms) during the 180 day follow up period will be given an ACT plus PQ 0.5mg/kg for 14 days as rescue medication. These subjects will continue to be monitored for safety and efficacy at all scheduled visits through Day 180. Details of rescue medication including reason for the rescue medication will be recorded in the eCRF. Rescue medication will be sourced locally.

### **6.9.2. Prohibited Medications and Non-Drug Therapies**

The following drugs are prohibited for use from 30 days prior to screening:

- Anti-malarials and other medicines with known anti-malarial activity.
- Drugs with hemolytic potential.
- Drugs other than PQP known to prolong the QTc interval.
- Drugs known to interact with DHA-PQP or primaquine (refer to Eurartesim and primaquine SmPCs).
- Drugs excreted via renal transporters MATE, MATE2-K and OCT2.

Results from an *in vitro* renal transporters study showed that tafenoquine inhibits the renal transporters MATE1, MATE2-K AND OCT2. Inhibition of these transporters may explain mild, transient, asymptomatic increases of creatinine observed in previous clinical studies and may lead to increased exposure to medications excreted via these transporters. The following drugs are therefore prohibited for use from 30

days prior to study entry and for a period of 21 days following the blinded dose of tafenoquine.

- Anti-diabetic drugs of the biguanide class:
  - Phenformin
  - Buformin
- Anti-arrhythmic drugs:
  - Dofetilide
  - Procainamide
  - Pilsicainide

Metformin, another biguanide anti-diabetic, may continue to be taken provided the subject has serum creatinine below the upper limit of normal and has no concomitant medical condition that increases the risk of lactic acidosis.

The use of herbal remedies during the course of the study should be avoided. However, if taken this should be recorded in the eCRF under concomitant medication.

See [Appendix 5](#) in Section 12.5 for a non-exhaustive list of prohibited medicines and further guidance.

## 7. STUDY ASSESSMENTS AND PROCEDURES

Protocol waivers or exemptions are not allowed with the exception of immediate safety concerns. Therefore, adherence to the study design requirements, including those specified in the Time and Events Table, are essential and required for study conduct.

This section lists the procedures and parameters of each planned study assessment. The exact timing of each assessment is listed in the Time and Events Table (Section 7.1).

The following points must be noted:

- If assessments are scheduled for the same nominal time, THEN the assessments should occur in the following order:
  1. 12-lead ECG
  2. vital signs
  3. blood draws.

Note: The timing of the assessments should allow the blood draw to occur at the exact nominal time.

- The IRB/IEC would be informed of any safety issues that require alteration of the safety monitoring scheme or amendment of the Informed Consent Form.
- No more than 150mL of blood will be collected over the duration of the study, including any extra assessments that may be required.

**7.1. Time and Events Table**

Procedures	Visit Day (Treatment Period Days 1-14)															
	1	1		2 b	3	4	5	6	7	8	9	10	11	12	13	14
	Pre DHA-PQP	DHA-PQP	Blinded med a													
Written Informed Consent	x															
Subject Demography	x															
Medical History	x															
Disease History	x															
Signs & Symptoms	x	x														
Therapy History	x															
Inclusion/Exclusion Criteria	x															
Efficacy Assessments																
Blood smears	x			x c	x c				x							x
Plasmodium PCR genotyping/sequencing	x															
Safety Assessments																
Concomitant Medication	x	x		x	x	x	x	x	x	x	x	x	x	x	x	x
Physical Examination	x			x	x				x							
Vital Signs d	x			x	x o				x							x
12-lead ECG e	x				x				x							
Adverse Events f			x	x	x	x	x	x	x	x	x	x	x	x	x	x
Serious Adverse Events g	x	x		x	x	x	x	x	x	x	x	x	x	x	x	x
G6PD (phenotyping) h	x															
G6PD/CYP2D6 (genotyping) i	x															
Laboratory Assessments																
Hematology/Clin.Chem/urinalysis j	x				x		x		x							x
Methemoglobin l	x			x	x	x	x	x	x	x	x	x	x	x	x	x
PK sampling	x		x k						x							x
Investigational Product																
Dispense Open Label DHA-PQP		x		x	x											
Dispense Blinded Study Treatment (access IWRS on day 1 only)			x	x	x	x	x	x	x	x	x	x	x	x	x	x

## Time and Events Table (Continued)

Procedures	Visit Day (Follow Up Period)									
	21	28	60	90	120	150	180	195 p (only for subjects who have not relapsed prior to Day 180)	Relapse	Withdrawal from study
Window	-/+3d	-3d, +15d	-16 d, +15d	-14d, +15d	-14d, +15d	-14d, +19d	-/+10d	Day 180 + 15d to 21d		
Efficacy Assessments										
Parasitological Assessment (blood smears)	x	x	x	x	x	x	x		x	x
Plasmodium PCR genotyping/sequencing									x	
Safety Assessments										
Concomitant Medication	x	x	x	x	x	x	x	x	x	x
Physical Examination	x	x	x	x	x	x	x		x	x
Vital Signs d	x	x	x	x	x	x	x		x	x
12-lead ECG e		x							x	x
Adverse Events	x	x	x	x	x	x	x	x	x	x
Serious Adverse Events	x	x	x	x	x	x	x	x	x	x
Dispense rescue treatment (ACT+PQ)									x	
Laboratory Assessments										
Hematology/Clinical Chemistry	x	x	x	x	x				x m	x m
Methemoglobin l	x	x	x						x	x
PK Sampling		x	x						x n	
Open Label Primaquine										
Dispense open label PQ –only for subjects who have not relapsed prior to D180							x			

Time and Event Table Notes:

- a) Blinded study treatment may be started on Day 1 or Day 2. If started on Day 2, blinded primaquine/placebo is given from Day 2-15.
- b) If a subject starts blinded study treatment on Day 2, the following assessments should be completed on Day 15: Concomitant medication, AEs/SAEs, methemoglobin, dispense blinded study treatment.
- c) Blood smears to be taken twice daily until two consecutive negative smears 6-12 hours apart.
- d) Vital signs include height and weight (screening only), blood pressure, temperature, heart rate and respiratory rate.
- e) ECGs will be done in triplicate on Day 1 (prior to DHA-PQP). Subsequent ECGs will be done as single ECGs unless prolonged QTcF is seen. ECG timings post baseline will be as follows: 1) Before the last of the three daily doses of DHA-PQP 2) 4 hours (window -1 to +2 hours) after last dose of DHA-PQP, 3) Day 7, 4) Day 28 and 5) relapse/withdrawal if within 28 days post-dose.
- f) Adverse events are recorded from the time of the first dose of study treatment.
- g) Serious adverse events are recorded from the time of consent in order to fulfil international regulatory requirements.
- h) G6PD phenotyping to be performed by suitable qualitative test (refer to SRM) and quantitative spectrophotometric analysis.
- i) Blood sample to be collected for CYP2D6 genotyping and stored for possible G6PD genotyping. Sample for G6PD genotyping may be analyzed in the event of an SAE due to hemoglobin decline where a repeat G6PD phenotype assay would not define G6PD status (e.g. transfusion given or high reticulocyte count).
- j) Dipstick urinalysis to be only done at screening.
- k) PK samples must be taken 6-12 hours and 24-48 hours post blinded dose of tafenoquine.
- l) Methemoglobin will be measured daily up to Day 14, alternate days up to Day 28 and on Day 60.
- m) Hematology/clinical chemistry to be done at relapse/withdrawal (up to Day 120 only).
- n) PK will be done as close to the time of relapse as possible (up to Day 60 only).
- o) Vital signs on Day 3 will be done immediately after ECGs (ie before the last of the three daily doses of DHA-PQP and 4 (-1 to +2) hours after the last dose of DHA-PQP).
- p) The D195 assessment is only required for subjects who do not relapse prior to D180 and receive open label primaquine (0.5mg/kg daily for 14 days) at the end of the study. Subjects who have relapsed prior to Day 180 will complete the study at D180.

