## **9. STATISTICAL CONSIDERATIONS AND DATA ANALYSES**

### **9.1 Hypotheses**

The study is designed to test superiority of DHA-PQP plus TQ against DHA-PQP alone in the prevention of *P. vivax* malaria relapse. The null hypothesis for the primary endpoint is that the 6-month relapse-free efficacy is not different between the DHA-PQP plus TQ and DHA-PQP alone treatment groups. The alternative hypothesis is that the relapse-free efficacy of the treatments is different. The hypothesis test will be two-sided and tested at the 5% significance level.

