### **9.2 Sample Size Considerations**

#### **9.2.1 Sample Size Assumptions**

The sample size for the study is based on the comparison of the primary endpoint (i.e. relapse-free efficacy at 6 months post-dosing) between the DHA-PQP alone group versus DHA-PQP plus TQ. The comparison will be based on a Log rank test for the difference in relapse-free survival rates over 6 months using all the subjects in the intent to treat population.

It is assumed that the relapse-free efficacy will be 50% on DHA-PQP alone, 85% on DHA-PQP plus PQ, and 85% on DHA-PQP plus TQ. In order to detect a clinically meaningful difference of 35%, a sample size of 50 subjects per group will provide >90% overall power for the primary efficacy comparison, allowing for a 10% withdrawal rate. A trial of 150 subjects, with the given assumptions about DHA-PQP, DHA-PQP plus PQ, and DHA-PQP plus TQ relapse rates would expect to see 40 relapses: a combined relapse rate across all treatments of 26.7%. In addition, a DHA-PQP plus PQ arm will be used as a benchmark to help further interpret the observed relapse efficacy of DHA-PQP plus TQ.

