3.16	Safety	AE1CP	Summary of Adverse Events During the Double-Blind Treatment Phase Leading to Withdrawal from the Study by System Organ Class and Preferred Term	IDSL Order events in descending order by incidence in TQ+DHA-PQP arm only. Add footnote: 'Events are ordered based on incidence in TQ+DHA-PQP arm' Include total column.	Headline
3.17	Safety	AE1CP	Summary of Adverse Events During the Double-Blind Treatment Phase Leading to Discontinuation from Study Treatment by System Organ Class and Preferred Term	IDSL Order events in descending order by incidence in TQ+DHA-PQP arm only. Add footnote: 'Events are ordered based on incidence in TQ+DHA-PQP arm' Include total column.	Headline
3.18	Safety	AE1CP	Summary of Adverse Events of Special Interest During the Double-Blind Treatment Phase by System Organ Class and Preferred Term	Order events in descending order by incidence in TQ+DHA-PQP arm only. Add footnote: 'Events are ordered based on incidence in TQ+DHA-PQP arm' Include total column.	Headline
3.19	Safety	AE3	Summary of protocol defined Hb SAEs During the Double-Blind Treatment Phase		SAC

Safety: Tables					
No.	Population	IDSL / Example Shell	Title	Programming Notes	Deliverable
3.20	Safety	AE3	Summary of Grade 3 and Grade 4 Adverse Events During the Double-Blind Treatment Phase by Preferred Term	Include Grade 3 and Grade 4 events only. Order events in descending order by incidence in TQ+DHA-PQP arm only. Add footnote: 'Events are ordered based on incidence in TQ+DHA-PQP arm' Include total column.	SAC
Laboratory: Chemistry					
3.21	Safety	LB1	Summary of Chemistry Data	Present values for all treatment groups and valid lab parameters at each visit.	Headline
3.22	Safety	LB1	Summary of Chemistry Changes from Baseline	ICH E3 Present change from baseline values for all treatment groups and valid lab parameters at each visit.	Headline
3.23	Safety	LB15	Summary of Worst Case Chemistry Results Relative to Normal Range Post-Baseline Relative to Baseline	ICH E3	SAC
3.24	Safety	SAFE_T1	Summary of Clinical Chemistry Laboratory Data Outside the Reference Range (F3)		SAC
Laboratory: Haematology					
3.25	Safety	LB1	Summary of Haematology Data	Present values for all treatment groups and valid lab parameters at each visit.	Headline
3.26	Safety	LB1	Summary of Hematology Changes from Baseline	ICH E3 Present change from baseline values for all treatment groups and valid lab parameters at each visit.	Headline

Safety: Tables					

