No.	Population	IDSL / Example Shell	Title	Programming Notes	Deliverable
3.27	Safety	LB15	Summary of Worst Case Hematology Results Relative to Normal Range Post-Baseline Relative to Baseline	ICH E3	SAC
3.28	Safety	SAFE_T1	Summary of Haematology Laboratory Data Outside the Reference Range (F3)		SAC
3.29	Safety	SAFE_T2	Summary of Categories of Change from Baseline Haemoglobin (G/L) Data by Time		Headline
3.30	Safety	SAFE_T3	Summary of Haemoglobin Declines Over First 28 Days		SAC
Laboratory: Urinalysis					
3.31	Safety	UR1	Summary of Urinalysis Dipstick Results	IDSL	SAC
Hepatobiliary (Liver)					
3.32	Safety	LIVER1	Summary of Liver Monitoring/Stopping Event Reporting	IDSL	SAC
3.33	Safety	LIVER10	Summary of Hepatobiliary Laboratory Abnormalities	IDSL	SAC
ECG					
3.34	Safety	EG1	Summary of ECG Findings	IDSL	SAC
3.35	Safety	EG2	Summary of Absolute ECG Values by Visit	Include Heart Rate, RR Interval, QRS Duration, Uncorrected QT Interval and QTcF	SAC
3.36	Safety	EG2	Summary of Change from Baseline in ECG Values by Visit	IDSL Include Heart Rate, RR Interval, QRS Duration, Uncorrected QT Interval and QTcF	SAC
3.37	Safety	SAFE_T5	Summary of QTcF Values by Category and Visit		Headline
3.38	Safety	EG11	Summary of Maximum Increase in QTcF Values Post-Baseline Relative to Baseline Category over the First 7 Days		Headline

Safety: Tables					
No.	Population	IDSL / Example Shell	Title	Programming Notes	Deliverable
Vital signs					
3.39	Safety	VS1	Summary of Absolute Values in Vital Signs by Visit	ICH E3 Include Systolic Blood Pressure, Diastolic Blood Pressure, Mean Arterial Blood Pressure, Respiratory Rate and Temperature.	SAC
3.40	Safety	VS1	Summary of Change From Baseline in Vital Signs by Visit	ICH E3 Include Systolic Blood Pressure, Diastolic Blood Pressure, Mean Arterial Blood Pressure, Respiratory Rate and Temperature.	SAC
3.41	Safety	VS3	Summary of Worst Case Vital Sign Results Relative to Normal Range Post-Baseline Relative to Baseline	IDSL	SAC
Methaemoglobin					
3.42	Safety	LB1	Summary of Absolute Values in Methaemoglobin by Visit		SAC
3.43	Safety	LB1	Summary of Change From Baseline in Methaemoglobin by Visit		SAC

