11.11.5. Safety Figures

Safety: Figures					
No.	Population	IDSL / Example Shell	Title	Programming Notes	Deliverable
Adverse Events					
3.1	Safety	AE10	Common ($\geq 5\%$ in Any Treatment Group) Adverse Events and Relative Risk During the Double-Blind Treatment Phase	IDSL	SAC
Laboratory					
3.2	Safety	LB11	LFT Profile Plots	
Only for subjects with >3 ULN in ALT or AST. Add footnote to this effect. The subject ID, treatment group, sex, age and race should be included as a header for each subject's plot. Include Alk. Phos, ALT, AST, Total Bili., and Indirect Bili.
	SAC
3.3	Safety	LB11	Haematology Profile Plots	
Only for subjects with a $>30\text{g/L}$ decline from baseline haemoglobin or found to be G6PD deficient Add footnote to this effect. The subject ID, treatment group, sex, age and G6PD status should be included as a header for each subject's plot. Parameters to include are haemoglobin, reticulocytes (if available), methaemoglobin and bilirubin results (total and indirect bilirubin on same plot)
	SAC

Safety: Figures					
No.	Population	IDSL / Example Shell	Title	Programming Notes	Deliverable
3.4	Safety	LB11	Clinical Chemistry Profile Plots	
Only for subjects change from baseline in urea or creatinine > 50% Add footnote to this effect.
 
The subject ID, treatment group, sex, age and race should be included as a header for each subject's plot.
 
Parameters to include are creatinine and urea (present the results relative to ULN).
	SAC
3.5	Safety	LB10	Distribution of Maximum LFTs by Treatment Group		SAC
3.6	Safety	LB7	LFT Shift from Baseline to Maximum Value		SAC
3.7	Safety	LB8	Matrix Display of Maximum LFT Values		SAC
3.8	Safety	SAFE_F1	Maximum Absolute Methaemoglobin Value Over 28 Days		SAC
3.9	Safety	LIVER14	Scatter Plot of Maximum vs. Baseline for ALT	IDSL	SAC
3.10	Safety	LIVER9	Scatterplot of Maximum ALT vs. Maximum Total Bilirubin	IDSL	SAC
Methaemoglobin					
3.11	Safety	SAFE_F2	Change from Baseline in Methaemoglobin over time	Display up to 28 days	SAC
Vital Signs					
3.12	Safety	LB9	Boxplot of Mean Arterial Blood Pressure by Timepoint and Treatment Group	IDSL Display LB9 includes the ULN and identifies subjects who have a value >2xULN. The ULN is not defined for arterial blood pressure, so this is not required. The figure should just include all of the data at each visit.	SAC

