	Degrees of Freedom	Wald Chi-Square	p-value
<hr/>			
CYP2D6 Activity Score [1]			
DHA-PQP Only	xx	x.xx	x.xxx
TQ+DHA-PQP	xx	x.xx	x.xxx
PQ+DHA-PQP	xx	x.xx	x.xxx

[1] Model fitted with CYP2D6 Activity Score + battalion separately for each Treatment.
Note: p-value from a 2-sided test presented.

Population: Microbiologic-Intent-to-Treat

Table EFF_T9

Number (%) of Subjects Within Each CYP2D6 Metaboliser Class

CYP2D6 Metaboliser Class	TQ+DHA-PQP (N=xx)	PQ+DHA-PQP (N=xx)	DHA-PQP only (N=xx)
Poor Metaboliser	xx (xx%)	xx (xx%)	xx (xx%)
Intermediate Metaboliser	xx (xx%)	xx (xx%)	xx (xx%)
Extensive Metaboliser	xx (xx%)	xx (xx%)	xx (xx%)
Ultra Metaboliser	xx (xx%)	xx (xx%)	xx (xx%)

Metaboliser class is determined from the CYP2D6 activity score (AS) as follows: Poor AS=0; Intermediate AS=0.5 or 1; Extensive AS=1.5 or 2; Ultra AS≥2.5.

Population: Microbiologic-Intent-to-Treat

Table EFF_T10

Summary of the Number of Relapses per Subject

	TQ+DHA-PQP (N=xx)	PQ+DHA-PQP (N=xx)	DHA-PQP only (N=xx)
Number of Relapses			
n	xx	xx	xx
0	xx (xx%)	xx (xx%)	xx (xx%)
1	xx (xx%)	xx (xx%)	xx (xx%)
2	xx (xx%)	xx (xx%)	xx (xx%)
3	xx (xx%)	xx (xx%)	xx (xx%)

CONFIDENTIAL

200894

Population: Safety

Table SAFE_T1
Summary of Chemistry Data Outside the Reference Range

Lab Test: <Parameter (units)>

Timepoint	Clinical Concern Category	TQ+DHA-PQP (N=xx)	PQ+DHA-PQP (N=xx)	DHA-PQP only (N=xx)
Day 1	n	xx (xx%)	xx (xx%)	xx (xx%)
	Low	xx (xx%)	xx (xx%)	xx (xx%)
	High	xx (xx%)	xx (xx%)	xx (xx%)
Day 3	n	xx (xx%)	xx (xx%)	xx (xx%)
	Low	xx (xx%)	xx (xx%)	xx (xx%)
	High	xx (xx%)	xx (xx%)	xx (xx%)
...				
Any Time On-treatment	n	xx (xx%)	xx (xx%)	xx (xx%)
	Low	xx (xx%)	xx (xx%)	xx (xx%)
	High	xx (xx%)	xx (xx%)	xx (xx%)

CONFIDENTIAL

200894

Population: Safety

SAFE_T2
Summary of Categories of Change from Baseline Haemoglobin (G/L) Data by Treatment and Time

Treatment	N	Visit	Haemoglobin drop	n	Mean	SD	Median	Min	Max
TQ+DHA-PQP	xx	Day 3	<=20 g/L	xx	xxx.x	xxx.xx	xxx.x	xx	xx
			>20 g/L to <=30 g/L	xx	xxx.x	xxx.xx	xxx.x	xx	xx
			>30 g/L	xx	xxx.x	xxx.xx	xxx.x	xx	xx
			<=20 g/L	xx	xxx.x	xxx.xx	xxx.x	xx	xx
			>20 g/L to <=30 g/L	xx	xxx.x	xxx.xx	xxx.x	xx	xx
			>30 g/L	xx	xxx.x	xxx.xx	xxx.x	xx	Xx

CONFIDENTIAL

200894

Population: Safety

SAFE_T3
Summary of Haemoglobin Declines over first 28 days

	TQ+DHA-PQP	PQ+DHA-PQP	DHA-PQP only	Total
Maximum decline from baseline				
<=20 g/L	xx (xx%)	xx (xx%)	xx (xx%)	xx (xx%)
>20 g/L to <=30 g/L	xx (xx%)	xx (xx%)	xx (xx%)	xx (xx%)

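### The worst-case and maximum laboratory displays have no time limit, so malaria-time values can enter for about three times as many DHA-PQP-alone men as tafenoquine men

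*Protocol*

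**What the plan says.** - **Sampling.** Protocol 7.1 schedules post-dose haematology and chemistry on Days 3, 5, 7, 14, 21, 28, 60, 90 and 120. Smears are also due at the visits on Days 7, 14, 21, 28, 60, 90 and 120, so a recurrence found at one of these comes with a laboratory sample. For the separate Relapse column, note m says "Hematology/clinical chemistry to be done at relapse/withdrawal (up to Day 120 only".
- **Follow-up after relapse.** Under Protocol 5.4 and 6.9.1.2, a man who relapses receives rescue treatment and keeps attending to Day 180. In SAP 11.4.1 the double-blind phase ends at the Day 180 visit, not at relapse.
- **Displays without a limit.** SAP 11.11.4 plans Table 3.23, "Summary of Worst Case Chemistry Results Relative to Normal Range Post-Baseline Relative to Baseline", and Table 3.27, "Summary of Worst Case Hematology Results Relative to Normal Range Post-Baseline Relative to Baseline". SAP 11.11.5 plans Figures 3.5 to 3.7, 3.9 and 3.10 on maximum liver tests, for example "Matrix Display of Maximum LFT Values". Shell SAFE_T1 (Tables 3.24 and 3.28) has a row per visit and a final row, "Any Time On-treatment", which is not defined for laboratory data.
- **Displays with a limit.** The protocol-defined haemoglobin drop is limited to 15 days (Protocol 7.5.1.1), haemoglobin declines to 28 days (Table 3.30), maximum methaemoglobin to 28 days (Figure 3.8) and maximum QTcF increase to 7 days (Table 3.38).
- **Slotting.** SAP 8.3 and 11.3.1 admit unscheduled and withdrawal-visit results to tables and figures only where the window holds no scheduled visit. Among several results that are not unscheduled, the earliest is used. The SAP does not say to which class the Relapse visit belongs.
- **Planned rates.** Protocol 9.2.1 assumes "relapse-free efficacy will be 50% on DHA-PQP alone, 85% on DHA-PQP plus PQ, and 85% on DHA-PQP plus TQ".

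**The concern.** A worst-case or maximum display takes the most extreme value over the whole sampled period. That period contains more malaria in one arm than in the other, because preventing malaria is what tafenoquine is meant to do.

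Protocol 4.6.2 says that *P. vivax* causes haemolysis and can lead to anaemia. Protocol 5.4.2 lists haemoglobin, bilirubin, AST and ALT among the tests used to look for haemolysis. A recurrence can therefore move the parameters on which an 8-aminoquinoline is judged. Samples after a recurrence may also reflect rescue treatment, which more DHA-PQP-alone men will receive.

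Both effects raise the count of extreme values mainly in the DHA-PQP-alone arm. In the only placebo-controlled safety comparison, that tilts these displays towards tafenoquine.

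The plan applies the opposite principle elsewhere. Malaria and its symptoms are kept out of the adverse event displays (Protocol 7.5.1.6, SAP 8.1.2), and the other extreme-value summaries are limited to early windows.

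**Working it through.** **Inputs.** Six-month relapse is 50% on DHA-PQP alone and 15% on TQ and on PQ, with 50 men per arm (Protocol 9.2.1). The last scheduled laboratory draw is Day 120 (Protocol 7.1). The analysis windows are those of SAP 11.3.1. The constant hazard is an assumption; the documents give no timing of relapse.

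**1. The plan's own figure.** 50 × (0.50 + 0.15 + 0.15) = 40 relapses, and 40/150 = 26.7%. This matches Protocol 9.2.1.

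**2. Men who relapse.**
- By six months: 25 against 7.5 per 50, ratio 0.50/0.15 = 3.3.
- By Day 120, using 1 − (1 − p)^(120/180): DHA-PQP alone 1 − 0.50^(2/3) = 0.370, or 18.5 men; TQ 1 − 0.85^(2/3) = 0.103, or 5.1 men. The ratio is 3.6.
- In the two scenarios of Protocol 9.2.2 the six-month ratios are 0.50/0.20 = 2.5 and 0.45/0.15 = 3.0. The Day 120 ratios are 2.7 and 3.2.

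These count men who relapse, not men with a tabulated abnormality.

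**3. Does the extra relapse draw reach the tables?** It depends on an undefined term.
- If the Relapse visit is unscheduled and scheduled visits are attended, the extra draw enters no table or figure.
- If it is not unscheduled, it enters when it comes before the scheduled visit in its window. That means relapses on Days 18–21, 25–28, 44–60, 76–90 and 106–120. Under a constant hazard from Day 1 this is about 7.3 of 18.5 DHA-PQP-alone men and 2.1 of 5.1 TQ men, about 40%. If relapses start only after Day 28, it is about 47%.
- Samples at scheduled visits where a relapse is found enter on either reading.

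**4. Possible size.** Let q be the assumed chance that a captured relapse shows an abnormal value. If every relapse by Day 120 is captured, the excess on DHA-PQP alone is q × (37.0 − 10.3) points:

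| q | excess, points | men per 50 |
|---|---|---|
| 10% | 2.7 | 1.3 |
| 20% | 5.3 | 2.7 |
| 50% | 13.4 | 6.7 |

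For each q these are upper bounds, because capture will be incomplete.

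**5. Can masking be quantified?** Take a true doubling on TQ over a background rate b, with an assumed 75% of relapses by Day 120. The any-time rate is 1 − (1 − b)(1 − 0.50 × 0.75q) on DHA-PQP alone and 1 − (1 − 2b)(1 − 0.15 × 0.75q) on TQ.

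| b | q | DHA-PQP alone | TQ | observed ratio |
|---|---|---|---|---|
| 5% | 20% | 12.1% | 12.0% | 0.99 |
| 5% | 50% | 22.8% | 15.1% | 0.66 |
| 20% | 20% | 26.0% | 41.4% | 1.59 |
| 20% | 50% | 35.0% | 43.4% | 1.24 |

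The direction is the same throughout, but the size turns on b and q, and the documents give neither.

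**6. Effect of a 28-day limit.** By Day 28 a constant hazard gives 50 × (1 − 0.50^(28/180)) = 5.1 men and 50 × (1 − 0.85^(28/180)) = 1.2 men. The difference falls from 13.4 men per 50 to 3.9.

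**The case against.** The strongest reply is that the slotting rules, and the limits already set on the key safety summaries, leave little room for harm. Several parts of it stand.

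- **The extra draw.** A reader might infer from note m that the relapse-triggered sample is itself the main source of imbalance. The slotting rules do not support that: they keep out all of these draws on one reading and more than half on the other. Note m is ordinary safety monitoring, not an error.
- **The any-time row.** A reader might take it to run past treatment. The SAP does not say so. Shell SAFE_T4, which separates liver events during treatment from those after stopping, points if anything to a narrower meaning. The row is undefined, not shown to be wrong.
- **Loss of a real effect.** A reader might infer that a true doubling would vanish. That needs a low background rate. Every man enters with parasitaemia and is sampled on Days 3, 5 and 7, so the background could be well above 5% in all arms. Recurrences also include symptom-free positive smears treated promptly, so q may be small, above all for strict limits such as haemoglobin below 7 g/dL.
- **Other protection.** The haemoglobin-decline, methaemoglobin and QTcF extremes are already limited in time. Tables 3.21, 3.22, 3.25, 3.26 and 3.29 and the visit rows of SAFE_T1 show Days 3 to 28 separately. The displays at issue are descriptive.

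What the reply does not remove is that Tables 3.23 and 3.27 and the maximum liver-test figures have no limit, and that samples at scheduled visits where relapse is found enter them on any reading.

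**Conclusion.** The concern holds for a defined set of displays: Tables 3.23 and 3.27, Figures 3.5 to 3.7, 3.9 and 3.10, and, depending on an undefined term, the last row of SAFE_T1 in Tables 3.24 and 3.28. On the planned rates, malaria-time values can enter for about three times as many DHA-PQP-alone men as TQ men (2.5 to 3.6 across the planning scenarios). The Day 120 figures assume a constant hazard. Carrying the ratio over to tabulated men also assumes that relapses are picked up at scheduled visits equally often in each arm.

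The bias runs one way: it can understate a TQ laboratory effect against DHA-PQP alone. It does not apply to TQ against PQ, which share the planned 15% relapse rate. The amount of masking cannot be derived from the documents, and early effects stay visible by visit. This should be corrected, but it does not undermine the safety analysis as a whole.

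**What to change.** In the SAP:

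1. Add to Tables 3.23, 3.24, 3.27 and 3.28 and to Figures 3.5 to 3.7, 3.9 and 3.10 a row or panel limited to the first 28 days, matching the haemoglobin and methaemoglobin displays. Keep the full-period version and label it *including after relapse and rescue*. A calendar limit is the same for every arm and does not condition on relapse. Say whether it means study days or the Day 28 analysis window, which runs to Day 43.
2. Define on-treatment for laboratory data.
3. State whether the Relapse visit counts as scheduled or unscheduled for slotting.

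The cost is wording and one extra row or panel per display, with no new data. The downside is that an effect arising after Day 28 would appear only in the full-period and by-visit displays.
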